Title	A Multicenter, Partially-Masked, Randomized, Controlled Study of Medical Therapy vs. Medical Therapy plus Optic Nerve Sheath Fenestration vs. Medical Therapy plus Stereotactic Ventriculoperitoneal Cerebrospinal Fluid Shunting in Subjects with Idiopathic Intracranial Hypertension and Moderate to Severe Visual Loss (“SIGHT”)
Précis	Randomized trial of adults (≥ 18 years old) with idiopathic intracranial hypertension and moderate to severe visual loss without substantial recent treatment who are randomly assigned to (1) medical therapy, (2) medical therapy plus ONSF, or (3) medical therapy plus VPS. The primary outcome is visual field mean deviation change at first of Month 6 (26 weeks) or time of treatment failure of the eligible eye(s), followed by a continuation study to assess time to treatment failure. The determination of eligible eye(s) is based on meeting the eligibility criteria at baseline.
Study Objectives	
Primary objective: to determine whether the efficacy of stereotactic ventriculo-peritoneal CSF shunting (VPS) with medical therapy is superior to medical therapy alone or optic nerve sheath fenestration (ONSF) with medical therapy in reducing or reversing visual loss in subjects with idiopathic intracranial hypertension and moderate to severe visual loss.
 
Secondary objective: To assess time to treatment failure over up to 3 years.

Study Design	
Multi-center randomized single-masked phase 3 clinical trial
 
 • RCT is followed by a treatment failure identification phase (up to 3 years of follow-up total)
Number of Sites	~40 sites
Endpoint	
Primary Efficacy Outcome:
 
 • Change from baseline to first of Month 6 (Week 26) or time of treatment failure in PMD (perimetric mean deviation) in eligible eye(s) with the size V stimulus. 
Key Secondary Efficacy Outcomes:
 
 • Time from randomization to treatment failure • CSF pressure measurement by lumbar puncture • Papilledema grade • OCT measures • QOL assessments • Visual field examination ratings (improved, remained the same, or worsened) 
Key Safety Outcomes: Vision loss, all reported adverse events
 
Other Key Outcomes: Change in weight

PARTICIPANT AREA	DESCRIPTION

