1.8.1 Randomized Trial

		Safety Visit ¹	Safety Visit ¹						Primary Outcome
Overview of Study Procedures	SC/BL Visit (-3-0 days)	S Visit 1 wk ±4 days	S Visit 2 wks ±4 days	Visit 1 4 wks ±7 days	Visit 2 8 wks ±7 days	Phone call 12 wks ±7 days	Visit 3 16 wks ±7 days	Phone call 20 wks ±7 days	Visit 4 26 wks ±7 days
Written Informed Consent	X								
Eligibility Criteria	X								
Med/IIH History/Update	X			X	X		X		X
Physical Exam	X								
Lumbar Puncture	X								X
Questionnaires	X								X
Vital Signs with weight	X	X	X	X	X		X		X
Ocular Exam	X ²	X	X	X	X		X		X
Refraction/Acuity	X	X	X	X	X		X		X
Perimetry	X ³	X	X	X	X		X		X ³
Fundus Photographs	X		X	X	X		X		X
OCT	X ⁴	X	X	X	X		X		X ⁴
CBC with platelet count	X						X		X
Metabolic panel w LFTs, amylase and electrolytes	X						X		X
Electrolyte testing ⁵				X	X		X		X
Blood sample for storage	X								
Pregnancy test	X								
Adverse Events	X	X	X	X	X	X	X	X	X
Concomitant Drug Therapy	X	X	X	X	X	X	X	X	X
Randomization	X								

		Safety Visit ¹	Safety Visit ¹						Primary Outcome
Overview of Study Procedures	SC/BL Visit (-3-0 days)	S Visit 1 wk ±4 days	S Visit 2 wks ±4 days	Visit 1 4 wks ±7 days	Visit 2 8 wks ±7 days	Phone call 12 wks ±7 days	Visit 3 16 wks ±7 days	Phone call 20 wks ±7 days	Visit 4 26 wks ±7 days
Dispense/prescribe acetazolamide	X			X	X		X		X
Prescribe furosemide/potassium as needed				X	X		X		X
Review Drug Compliance		X	X	X	X	X	X	X	X
Dietary Counseling	X			X	X		X		X

409 ¹Timing of 1 week and 2 week safety visits dependent on treatment group (timing for medical therapy group relative to randomization and timing for surgery groups relative to
 410 surgical procedure). The 2 week visit could be skipped if there is marked improvement (see section 5.1.2). One or both safety visits will be repeated after each surgical procedure.

411 ² IOP must be measured at Screening to assess eligibility

412 ³Two sets of FT size V at Screening; same requirement for week 26.

413 ⁴If LP performed, OCT should be performed prior to LP. Another set of OCT testing after LP is optional at Screening.

414 ⁵For subjects taking furosemide, will be done at local lab prior to each dose increase, once the final dose is reached, and then at each visit

415

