963 *The 26 Week OCT must be done *before* the lumbar puncture.

964 **5.1.4 Phone Contact Procedures**

965 The Site Coordinator will contact the subject by telephone to review adverse events.

- 966 • Medical/IIH History update
- 967 • Adverse Events
- 968 • Review of Concomitant Medications
- 969 • Review of Drug Compliance

970 Additional phone contacts, texts, and emails may be performed as needed.

971 **5.1.5 Safety Visit Procedures**

972 The following procedures will be performed for all subjects at each safety visit:

- 973 • Adverse Events
- 974 • Concomitant Medications
- 975 • Vital signs, including weight
- 976 • Refraction
- 977 • Visual Acuity
- 978 • Ocular Examination
- 979 • Humphrey Visual Field testing with 24-2 full-threshold program using size V stimulus
- 980 • OCT (optic nerve head and macula)
- 981 • Fundus Photographs (only at week 2)
- 982 • Drug Compliance/Accountability

983 **5.2 Treatment Failure Identification Phase**

984 **5.2.1 Follow-up Visits**

985 Follow-up visits will occur at weeks 52 (12 months), 104 (2 years), and 156 (3 years) +4 weeks
986 as long as the study is ongoing.

987 **5.2.2 Study Visit Procedures**

988 Procedures at these visits will include the following:

- 989 • Medical/IIH history update (includes all new treatments and adjustments of dosages)
- 990 • Adverse Events
- 991 • Concomitant Medications
- 992 • Vital signs, including weight
- 993 • Refraction
- 994 • Visual Acuity
- 995 • Ocular Examination
- 996 • Humphrey Visual Field testing with 24-2 full-threshold program using size V stimulus
- 997 • Fundus Photographs
- 998 • OCT (optic nerve head and macula)
- 999 • Drug Compliance
- 1000 • QoL questionnaires – at study site or online
- 1001 • HIT-6 questionnaire – at study site or online

1002 If subject wants to discontinue birth control after the 6-month RCT, this should be discussed with
1003 the Site Investigator.

1004 **5.2.3 Phone Contact Procedures**

1005 A phone, text or email contact will occur at 39 weeks by site staff. Subsequent contacts (every 3
1006 months, starting at month 15 through month 33) will be by Coordinating Center staff for a
1007 structured interview to determine if IIH symptoms have worsened. If the caller has concerns
1008 about the subject, the site investigator will be notified and will be responsible for contacting the
1009 subject.

1010 **5.3 Unscheduled Visits**

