1070 **5.7.1 Treatment Failure Criteria**

1071 If either of the below criteria for worsening are met, the subject will be considered for treatment
1072 failure by the Adjudication Committee:

- 1073 1. Worsening of Full Threshold Size V 24-2 Perimetry.
- 1074 a. Average baseline MD is equal to or better than -4 dB and visual function worsens
1075 more than 2 dB MD from the baseline average.
- 1076 b. Average baseline MD is worse than -4 dB and equal to or better than -6 dB and
1077 visual function worsens more than 3 dB MD from baseline average.
- 1078 c. Average baseline MD is worse than -6 dB and visual function worsens more than
1079 4 dB MD from baseline average.
- 1080 2. Worsening of 2 or more lines of ETDRS visual acuity

1081 **5.7.2 Treatment Failure Review by Adjudication Committee**

1082 The Adjudication Committee will review possible treatment failures and determine if a treatment
1083 failure has occurred. The committee will be masked to treatment assignment and using all
1084 available clinically-related information, including fundus photo results, will decide whether the
1085 failure is most likely due to increased intracranial pressure or from another cause, such as
1086 perimetric artifact, poor subject effort, or the presence of another unrelated cause of visual loss.

1087 If the Adjudication Committee determines that a possible treatment failure is most likely due to
1088 IIH, the subject will be classified as having experienced a treatment failure. All cases that are
1089 sent to the Adjudication Committee will be reviewed first by the Study Director. If it is obvious
1090 that the patient meets criteria for treatment failure, they will be so designated. The case will
1091 subsequently be reviewed by the Adjudication Committee.

1092 When a subject meets the criteria for treatment failure, it is preferred that subsequent therapy
1093 come from one of the other two treatment arms but this decision will be deferred to the judgment
1094 of the Site Investigator. These subjects will continue to be followed at their set times for the full
1095 follow-up period (up to 3 years). The date of a confirmed treatment failure will be the date of the
1096 first visual field that triggered the Adjudication Committee review.

1097 If treatment failure is not confirmed, the subject will continue to follow his/her treatment group's
1098 protocol.

1099

[figure not shown]
1100

Figure 3. Algorithm for Review by Surgical Malfunction Review Committee

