490 treatment group comparisons. Likewise, likelihood ratio tests will be performed for the
491 significance of these hazard ratios using a Bonferroni-adjusted two-tailed significance level of
492 1.7%. Kaplan-Meier curves will be used to describe the cumulative probability of treatment
493 failure over time in each treatment group.

494
495 For subjects who do not experience the outcome, event times will be censored at the last subject
496 contact at which the subject was determined to not have experienced the outcome (e.g., at time of
497 premature withdrawal from the trial or at the final trial visit).
498

499

500 **3.6.2 Adjustment for Baseline Covariates**

501 Adjustment for additional baseline covariates (in addition to baseline PMD and papilledema
502 grade in best eligible eye) may be considered depending on the comparability of the treatment
503 groups at baseline (refer to *Section 3.2.3*).
504

504

505 **3.6.3 Investigation of Treatment by Covariate Interactions**

506 Examination of interactions between treatment group and selected baseline covariates will be
507 performed using the Cox proportional hazards model following the guidelines established in
508 *Section 3.2.4*.
509

509

510 **3.6.4 Verification of Model Assumptions**

511 The underlying assumptions of the Cox proportional hazards model will be checked and a
512 thorough analysis of the martingale residuals and other diagnostics will be performed. Remedial
513 measures (covariate transformation) will be taken if serious violations of these assumptions are
514 detected.
515

515

516 The proportional hazards assumption will be assessed graphically by plotting $\log(-\log(\hat{S}(t)))$ vs.
517 $\log(\text{time})$ for each of the treatment groups, and by examining plots of smoothed Schoenfeld
518 residuals. The assumption also will be examined by dividing the time scale into 6-month periods
519 and estimating the treatment group hazard ratios separately in each of these periods through the
520 use of time-dependent covariates. The period length of 6 months may be adjusted prior to
521 unmasking, based on the observed distribution of event times, if relatively few events occur
522 during 6-month periods. Treatment group comparisons will be described in this manner if the
523 proportional hazards assumption appears to be seriously violated.
524

524

525 The assumption of independence between censoring time and the (unobserved) event time will

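### The 6-month periods for period-specific hazard ratios cut through the windows of the Week 26, 52 and 104 visits and leave two periods with no scheduled visual field

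*SAP*

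**What the plan says.** SAP 3.6.4 gives three checks of proportional hazards for time from randomization to treatment failure: a log-log plot, smoothed Schoenfeld residuals, and a division of time. On the third it says "The assumption also will be examined by dividing the time scale into 6-month periods" "and estimating the treatment group hazard ratios separately in each of these periods through the" use of time-dependent covariates. "The period length of 6 months may be adjusted prior to" unmasking, but only if few events fall "during 6-month periods. Treatment group comparisons will be described in this manner if the" proportional hazards assumption looks seriously violated. Protocol 9.7 says the same. Neither text says whether the periods are open or closed at the cut, or whether the last one ends at 36 months.

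On timing:
- The protocol summary equates Month 6 with week 26: "change at first of Month 6 (26 weeks) or time of treatment failure". The schedule in protocol 1.8.1 has "Visit 4 26 wks ±7 days".
- Protocol 5.2.1 has "Follow-up visits will occur at weeks 52 (12 months), 104 (2 years), and 156 (3 years"). The schedule in 1.8.2 gives windows of ±7 days at week 52 and ±4 weeks at weeks 104 and 156.
- Protocol 5.7.2 dates a confirmed failure by the "first visual field that triggered the Adjudication Committee review".

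**The concern.** From Week 26 on, visual fields are scheduled only at weeks 26, 52, 104 and 156. The first three coincide with the cuts at months 6, 12 and 24. Two patients with the same course, both found to have failed at the Month 6 visit, fall in different periods if one attends on day 180 and the other on day 185. Two of the six periods contain no nominal visit. Scheduled fields reach them only through late attendance at the visit before, so their events come from late attenders and unscheduled visits.

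At stake is the reading of early against late effect. Protocol 1.4.2 calls time to treatment failure very important because a benefit at 6 months may not last. Period-specific hazard ratios are meant to show such a change. With these cuts, a ratio labelled as one period's effect can largely be that of the period before.

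**Working it through.** The plan gives no event count, hazard ratio or power for this analysis, so there is no stated figure to reproduce.

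**1. Cuts against visits.** Counting 6 months as 26 weeks, the interior cuts are days 182, 364, 546, 728 and 910. The visits at weeks 26, 52 and 104 are days 182, 364 and 728, each 0 days from a cut. Counting calendar half-years (182.625 days), the cuts near these visits are days 182.6, 365.25 and 730.5, which miss them by 0.6, 1.25 and 2.5 days. All lie inside the windows.

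**2. Share of each window after the cut.** Share = (window end − cut) / window length, with even attendance over the schedule's windows.

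| Visit | Window (days) | Calendar months | 26-week multiples |
|---|---|---|---|
| Week 26 | 175-189 | (189 − 182.625)/14 = 46% | 7/14 = 50% |
| Week 52 | 357-371 | (371 − 365.25)/14 = 41% | 7/14 = 50% |
| Week 104 | 700-756 | (756 − 730.5)/56 = 46% | 28/56 = 50% |

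Counting whole days gives 40-49%. SAP 3.2.1 also accepts Month 6 outcome fields on days 168-242. Of those 75 days, 60 (80%) fall after day 182, although that window governs the primary outcome and not the failure date.

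**3. Nominal visits per period.** Weeks 0-26: 1, 2, 4, 8, 16 and 26. Weeks 26-52: 52. Weeks 52-78: none. Weeks 78-104: 104. Weeks 104-130: none. Weeks 130-156: 156.

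**4. Effect on the estimates (illustration).** A large-sample simulation used 60,000 subjects in two arms, a reference hazard of 0.004 per week, attendance uniform over the windows, and a Cox model with Efron ties in each period. The hazards, hazard ratios and detection shares are assumptions and do not come from the documents. A stated share of failures is found at once at unscheduled visits; the rest wait for the next scheduled field.

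| Weeks | 0-26 | 26-52 | 52-78 | 78-104 | 104-130 | 130-156 |
|---|---|---|---|---|---|---|
| True | 0.5 | 0.5 | 1.0 | 1.0 | 1.5 | 1.5 |
| 0% at once | 0.51 | 0.51 | **0.48** | 1.00 | **1.02** | 1.46 |
| 30% at once | 0.47 | 0.51 | **0.71** | 1.02 | **1.16** | 1.48 |
| 60% at once | 0.50 | 0.49 | **0.87** | 1.00 | **1.36** | 1.46 |

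The two periods without a visit return the previous interval's ratio when all failures are found at scheduled visits. They move towards the truth as unscheduled detection rises.

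**5. Does a longer period cure it?** Twelve-month periods still cut at weeks 52 and 104, dividing the window days 8 to 7 and 29 to 28.

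**6. Where between visits to cut.** Suppose a failure found at a scheduled visit began at any time since the previous nominal visit, with equal chance. The share beginning before the period to which it is assigned is then:

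| Visit | Midpoint cuts (weeks 39, 78, 130) | Cuts just after the window (day 243, weeks 57, 109) |
|---|---|---|
| Week 52 | 13/26 = 50% | (243 − 182)/182 = 34% |
| Week 104 | 26/52 = 50% | 5/52 = 10% |
| Week 156 | 26/52 = 50% | 5/52 = 10% |

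Both sets keep every window whole. The midpoints at weeks 78 and 130 also fall on the month 18 and month 30 telephone contacts, which can prompt a field. In the same simulation, midpoint cuts gave 0.62 and 0.71 for weeks 39-78 with 30% and 60% found at once, a blend of the true 0.5 and 1.0. The later cuts were not simulated.

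**The case against.** The strongest reply is that the consequence is small. The two graphical checks do not use the cuts, nor do the main Cox model and the Kaplan-Meier curves. The period ratios become the reported form only after a serious violation, for a secondary outcome. That stands, and it sets the priority.

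Second, the plan allows the length to change, and sparse periods are plausible: it expects at most 15% of subjects, or 0.15 × 180 = 27, to fail before Month 6. Nine-month periods would cut at weeks 39, 78 and 117, clear of the three windows. The clause therefore permits a remedy. It does not require one, it applies only if events are few, and it concerns length and not position.

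Third, detection between visits is built in. Protocol 5.3 and 5.4 allow unscheduled visits and extra assessments, 5.2.3 adds quarterly contacts from month 15 to month 33, and reoperation brings safety visits with perimetry. These lessen the distortion. The quarterly contacts are interviews without perimetry, and in the illustration bias remains with 60% found at once.

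Fourth, SAP 3.6.1 calls the times discrete, which might suggest nominal visit times and no splitting. It says so only to justify Efron ties, while protocol 5.7.2 dates failure by the actual field. Nominal times would still leave two periods without a visit.

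A reader might infer more than the documents support:
- That 41-50% of failures are placed in the wrong period by onset. The figure is a share of the window, and onset is unobserved. Under even onset since week 52 and calendar months, the Month 24 share would be 46% + 54%/2 = 73%.
- That week 156 is split in the same way. It ends follow-up and is not an interior cut.
- That one arm attends later. Protocol 5.1.1 times the randomized-trial visits from randomization in all three groups, and nothing suggests a difference.
- That the protocol expects proportional hazards to fail. Section 1.4.2 only explains why long follow-up matters.

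**Conclusion.** The concern holds. Applied as written, the 6-month rule divides failures found at the Week 26, 52 and 104 visits by appointment timing, and gives weeks 52-78 and 104-130 hazard ratios that tend to repeat the preceding interval's effect. About 41-50% of each window lies after the cut, depending on how 6 months is counted. This assumes evenly used windows and actual failure dates. The size of the bias depends on how many failures are found between visits, which the documents do not state. The simulated values show its direction and are not a forecast. The primary analysis and the overall hazard ratios are not affected. The change is worth making because it is nearly free, but its priority is modest.

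**What to change.** In SAP 3.6.4 and protocol 9.7, before unmasking, replace the 6-month periods with periods whose cuts lie between scheduled visits and clear of their windows, preferably just after each window closes. For example: randomization to day 243, day 243 to week 57, week 57 to week 109, and week 109 to the end of follow-up, left open. Each period then holds one of the visits at weeks 26, 52, 104 and 156 with its whole window, including days 168-242. State which side of the cut is closed and that actual dates are used. Describe each ratio as referring to failures detected in that inter-visit interval, and apply the same rule to any later merging.

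The week 52 window should also be reconciled. The schedule gives ±7 days and protocol 5.2.1 prints plus 4 weeks, where a ± sign may have been lost. The example cut at week 57 (day 399) clears either reading, since 364 + 28 = 392.

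The cost is a few sentences, with no new data. The downside is four unequal periods in place of six equal ones, and onset within an inter-visit interval remains unknown.
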